## 8. Reporting of Adverse Events

This study includes 2 behavioral interventions (texting and CHW counseling) as well as completing surveys. This is a minimal risk to participants. Care will be taken to protect the privacy of participants in this study. However, there is a risk that others may inadvertently see participants' research or medical information, and thus privacy may be compromised. In the unlikely event that a serious adverse event (SAE) is considered possibly, probably or definitely related to the study, or in the event of major incidents or major protocol violations, reporting to University of California-San Francisco IRB will be reported as outlined in Table 6. Suspected events will be reviewed by study investigators prior to submission to the IRB.

**Table 6. Event Reporting Timeline**

Institution	Type of Events	When to Report
UCSF Human Research Protections Program (HRPP)	Adverse events that UCSF PI determines are 1) serious, 2) related, and 3) unexpected or more frequent or severe than expected	
 
Most events: Within 5 working days of awareness
 
Related deaths and life-threatening events: Immediately
 

	Major protocol violations	Within 10 working days of awareness
	Major incidents	
 
Major incidents that are potential breaches of confidentiality: Within 48 hours
 
Other major incidents: Within 10 working days of awareness
 

## 9. Statistical Considerations

This study includes a developmental aim (Aim 1) to adapt interventions tested in Aim 2 and 3. Herein we present the statistical design and power for randomized trials in Aim 2 and 3.

In Aim 2, we will compare the effectiveness of two strategies—Arm 1: RSV vaccine information flyer at enrollment + text-message nudges vs. Arm 2: Community Health Worker (CHW) counseling *and* text message nudges—on RSV vaccine uptake among 400 Latino adults  $\geq$  50 years. In Aim 3, we will compare the effectiveness of two strategies: Arm 1: RSV vaccine information flyer at enrollment + text-message nudges vs. Arm 2: Community Health Worker (CHW) 'activation' counseling *and* text message nudges—on enabling participants (18-49 years old) to discuss RSV vaccination with older adults in their family and social network. We will conduct in-depth qualitative interviews with a subset of participants from Aim 2 and 3, with stratified sampling based on key outcome measures. We will also describe implementation outcomes for text-messaging and CHW counseling, using metrics that align with the RE-AIM framework.

## 9.1. Aim 1 Statistical Considerations

Aim 1 is primarily a qualitative study and developmental aim, but it includes one quantitative survey. We will use logistic regression to assess predictors of vaccine hesitancy with the primary outcome being unlikely to get or recommend the RSV Vaccine. Primary predictors include age, sex, acculturation level, preferred language.

## 9.2. Aim 2 (Motivate Trial) Statistical Considerations

**Study Design:** Two-arm randomized type-1 effectiveness-implementation individually randomized trial.

**Analysis Plan.** We will compare the primary outcome of RSV vaccine uptake within 60 days between the two study arms using two broad statistical approaches: unadjusted analyses to explore average treatment effects and model adjusted estimates to reduce variance and examine effects for subpopulations. First, we will examine the intention-to-treat (ITT) effect, over all participants, for the primary outcome of vaccine uptake using the Fisher exact test. To account for participants which the CHW may not be able to reach, we will examine the average treatment effect on the treated (ATT). Second, we will use targeted maximum likelihood estimation (TMLE), a pre-specified approach to data-adaptively adjust for stratified randomization factors and additional baseline predictors of the outcome in order to improve precision. RSV vaccine uptake will be ascertained through the California Immunization Registry, the medical record, or proof of vaccination from a pharmacy. Using an analogous approach, we will also compare intervention effectiveness on pre-specified secondary outcomes and within pre-specified subgroups: baseline high vaccine hesitancy, low trust of healthcare system, low acculturation (score<3.0), sex. These will be augmented by predictor analyses to elucidate risk factors for poor vaccine uptake, overall and by arm and exploratory machine learning analysis for treatment effect heterogeneity. Additionally, we will examine pathways of intervention action (i.e. direct and indirect effects) using formal mediation analyses, considering mediation by post-baseline trust and perceived benefits in the vaccine. Both predictor and mediation analyses will use TMLE.

**Implementation Outcomes:** We will calculate implementation outcomes using the RE-AIM framework for each, through quantitative and qualitative analyses.

**Analysis of qualitative data:** Interviews will be transcribed and analyze by the bilingual study team (Co-I, UCSF research staff, CHW) with a thematic analysis guided by initial analytic code list based on the Behavioral and Social Determinants (BeSD) of Vaccination Framework, quantitative survey results, and outcomes for the RE-AIM framework. As not all responses may not map onto BeSD determinants and other pre-determined themes, an inductive approach will also be used to generate sub-themes within the initial coding scheme. At defined stages of the analysis, codes and definitions will be refined or expanded as needed. In weekly team meetings, members will discuss coding of rich or difficult segments to achieve consensus.

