## 6. Study Intervention and Randomizations

### 6.1. Randomization (Aim 2 & 3)

Both Aims 2 and 3 are 2 arm trials and intervention groups are described in 4.3.3 (Aim 2) and 4.4.3 (Aim 2). After enrollment participants will then be randomized to one of two study groups. Randomization will be computer generated, block randomization with random block sizes of 2, stratified by sex.

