### 9.2.1. Aim 2 Sample Size Considerations

Based on our preliminary data and a national survey, we anticipate 28% RSV vaccine uptake in our text-only arm (20% with no intervention and 8% increase with text). Assuming complete data for the primary outcome of vaccine uptake reported by CAIR, the medical record, or proof of vaccination from a pharmacy and  $\alpha=0.05$ , our sample size of N=200 per arm will conservatively

provide a minimum detectable ITT effect size of 10%. Assuming CHWs will be able to reach 90% of participants assigned to the counseling arm, our sample will be able to provide a minimum detectable ATT of 10.9%; if participants assigned to counseling are particularly hard to reach and only 80% take part in CHW counseling, we will be able to provide a minimum detectable ATT effect 12.3%.

Statistical power for secondary outcomes will depend on participation in the 60-day follow-up survey. If 10% of participants are lost to follow-up, the minimum detectable effects increase to 10.6% for ITT, 11.5% for ATT if 90% of intervention arm participants receive counseling and 12.9% for ATT if 80% of intervention arm participants receive counseling. Under a setting of high loss to follow-up, where 20% of participants in both arms are not reached for a follow-up survey, the minimum detectable effects increase to 11% for ITT, 12.2% for ATT if 90% of intervention arm participants receive counseling and 13.7% for ATT if 80% of intervention arm participants receive counseling.

Estimated treatment effects for all outcomes will be improved with statistical modeling with TMLE.

In a nested secondary pre-post analysis we will compare the proportion of people who received the RSV vaccine prior to the text-message to 30 days after the text.

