### **9.3. Aim 3 (Activate Trial) Analysis Plan**

**Aim 3 Study Design:** Two-arm randomized type-1 effectiveness-implementation individually randomized trial.

**Aim 3 Analysis Plan:** We will take an analogous analytic approach to Aim 2 to evaluate our primary outcome, 'the average proportion of older adult contacts with whom RSV vaccination was discussed' between the two study arms' and secondary outcomes, together with pre-specified subgroup analyses (age group 18-29 vs. 30-49 years). We will also undertake additional social network analyses to assess the relationship between egocentric network characteristics and the odds of discussing RSV vaccination: network size, type of relationship (e.g grandmother vs. aunt), characteristics of the participant (e.g. lives in multigenerational household, vaccine confident, age, acculturation), by study arm and pooled across arms.

**Implementation Outcomes:** We will use definitions outlined in Table 2 and analogous quantitative and qualitative methods outlined in Aim 2.

In a nested secondary pre-post analysis we will compare the proportion of people who discussed the RSV vaccine with eligible family or friends prior to the text-message to 30 days after the text.

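### Aim 2 has two analyses of its primary outcome and no named confirmatory one; the first listed, an unadjusted Fisher exact test, costs about 4 points of power against a test that runs at 5%

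*Protocol*

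**What the plan says.** Section 9.2 sets out two approaches to 60-day vaccine uptake: "unadjusted analyses to explore average treatment effects and model adjusted estimates to reduce variance and examine effects for subpopulations". The first is the ITT comparison over all participants, "for the primary outcome of vaccine uptake using the Fisher exact test", with an average treatment effect on the treated to allow for people the CHW cannot reach. The second is TMLE, to "data-adaptively adjust for stratified randomization factors and additional baseline predictors of the outcome in order to improve precision". The section does not rank the two.

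Section 6.1 specifies "block randomization with random block sizes of 2, stratified by sex" for both trials. Sex is the only stratification factor.

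Section 9.2.1 supplies the design figures: "we anticipate 28% RSV vaccine uptake in our text-only arm", alpha 0.05, complete primary outcome data, and 200 per arm, for a minimum detectable ITT effect of 10%. It adds that TMLE will improve the estimates.

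For Aim 3, section 9.3 says "We will take an analogous analytic approach to Aim 2 to evaluate our primary outcome". That outcome is a mean of participant-level proportions.

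**The concern.** Two analyses of one primary outcome can disagree. By the calculation below, power for the protocol's own target difference is only about 53% to 57%, so results near the significance boundary are likely. An unadjusted p-value and an adjusted interval could then fall on opposite sides of 0.05, and the text gives no rule for which one counts. If the choice is made after unblinding, it is open to challenge.

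The listed order also favours the weaker method. Fisher's test makes no use of the factor on which the allocation is balanced, and it spends less than the nominal 5%. A more precise analysis is already planned for the same outcome.

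**Working it through.** **Inputs.** From section 9.2.1: 28% control uptake, 200 per arm, alpha 0.05, a 10-point effect (28% to 38%) and no missing primary outcome data. Two assumptions are needed. The protocol does not give sidedness, so I take two-sided. It does not give power for Aim 2, so I take 80%, the figure stated for Aim 3 in section 9.3.1.

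**Step 1: the plan's own figure.** Pooled normal approximation, with mean rate (0.28 + 0.38)/2 = 0.33:
- Standard error under the null: sqrt(2 × 0.33 × 0.67 / 200) = 0.0470.
- Standard error under the alternative: sqrt((0.28 × 0.72 + 0.38 × 0.62) / 200) = 0.0468.
- Power = Φ((0.10 − 1.96 × 0.0470) / 0.0468) = Φ(0.168) = 56.7%.

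The detectable difference at 80% power by this formula is 13.3 points. A 10-point difference needs 346 per arm. One-sided testing at 0.05 gives 68.6% power. The stated 10 points therefore does not reproduce under either reading, whichever test is used.

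**Step 2: Fisher against chi-square.** Enumerate all 201 × 201 outcome tables and sum the binomial probabilities of those each test rejects.

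| 200 per arm, two-sided 0.05 | Fisher exact | Pearson chi-square |
|---|---|---|
| True size, 28% in both arms | 3.90% | 5.03% |
| Power, 28% versus 38% | 52.7% | 56.8% |
| Detectable difference at 80% power | 13.7 points | 13.2 points |

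The cost of Fisher is 56.8 − 52.7 = 4.1 points of power and about 0.5 point of detectable difference. Its size stays between 3.6% and 4.0% for common rates from 14% to 50%, so the result does not hang on the 28% guess.

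**Step 3: how much is due to the unused sex strata.** This compares the sex-stratified Cochran-Mantel-Haenszel test with the unstratified chi-square, by simulation with half men and half women. The sex differences in uptake are assumptions.
- No sex difference: stratified power 56.7%, no gain.
- 10-point difference: 57.0%, a gain of up to about 0.3 point.
- 20-point difference: 58.4%, a gain of about 1.7 points. Fisher's size falls to about 3.4% here.

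Unless sex predicts uptake strongly, the loss is discreteness and not the strata.

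**Step 4: what covariate adjustment could add.** The protocol gives no predictive strength for any covariate, so this is an illustration only. The standardized effect is 0.10 / 0.0470 = 2.13. If covariates explain a share R² of outcome variance, power is roughly Φ(2.13 / sqrt(1 − R²) − 1.96):
- R² = 0: Φ(0.17), about 57%.
- R² = 0.10: Φ(0.285), about 61%.
- R² = 0.15: Φ(0.35), about 64%.

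Reaching 80% power for 10 points at 200 per arm would need a variance reduction of about 1 − 200/346 = 42%.

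**The case against.** The best defence is that Fisher's test is valid, needs no model and no covariate choices, and errs on the safe side. An unadjusted test followed by an adjusted estimate is a respectable arrangement, and ranking analyses is often left to the SAP, which is not at hand. All of this is fair. What remains is that the protocol itself names both methods for one primary outcome, lists the weaker first and leaves them unranked.

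Several stronger readings are tempting but not supported:
- **That the plan ignores the stratification.** It does not. The TMLE in section 9.2 adjusts for the stratified randomization factors. Only the Fisher analysis leaves sex out.
- **That Fisher decides the trial.** The protocol never says so, and describes the unadjusted analyses as exploring average effects. The 4-point loss applies to the confirmatory result only if Fisher is taken as confirmatory.
- **That Fisher explains the power shortfall.** A test running at 5% still has only about 57% power for 10 points.
- **That adjusted power will be 61% to 64%.** This rests wholly on an assumed R² of 0.10 to 0.15.
- **That Aim 3 is committed to Fisher.** The word used is analogous, and section 9.3.1 powers that outcome as a difference in means with SD 0.3, treating binary outcomes separately. The protocol just does not say what the analogous primary analysis is.

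**Conclusion.** The point holds in limited form. Section 9.2 gives two unranked analyses of the Aim 2 primary outcome. The first listed runs at 3.9% and costs about 4 points of power and half a point of detectable difference relative to a test that uses its full 5%. These figures assume two-sided testing at 0.05, 28% control uptake, complete data and, for the detectable difference, 80% power. The loss is one of efficiency, with no threat to type I error, and very little of it comes from leaving out sex. Any gain beyond about 4 points depends on covariate strength that the protocol does not give. The size is modest, but the trial is short of power and the remedy is nearly free, so the change is worth making.

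**What to change.** In section 9.2, name the covariate-adjusted ITT risk difference by TMLE as the single primary Aim 2 analysis. Keep sex in the adjustment set always, and fix the other baseline covariates and the learner before outcome data are seen. List the Fisher test, or a sex-stratified Mantel-Haenszel test, as sensitivity and the ATT as secondary.

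In section 9.3, state that the analogous Aim 3 primary analysis is a sex-adjusted comparison of participant-level mean proportions.

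The cost is a few sentences plus the work of settling covariates and learner, which the protocol now describes only as baseline predictors. No change to sample size or data collection is needed. The 10-point detectable effect in section 9.2.1 needs its own correction; this change does not supply it.

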#### Aim 2:

##### **Secondary:**

- RSV Vaccine uptake at 60 days (self-report)
- RSV Vaccine uptake at 90 days per CAIR or per medical record
- RSV Vaccine uptake at 6 months per CAIR or per medical record
- Median time to vaccination (days)
- Appointment made at 60 days in clinic or a pharmacy with intent to get RSV Vaccine per self-report
- Increase in RSV Vaccine confidence (BeSD indicator) by 1 point

- Increase in motivation to get RSV Vaccine (BeSD indicator) by 1 point
- Increase in RSV vaccine knowledge by 1 point (Likert scale): Before today how much did you know about the RSV vaccine (1 = nothing, 2= a little, 3= some, 4= a lot)
- Average proportion of social network contacts  $\geq 50$  years with whom participant discussed RSV vaccination at 60 days.
- Implementation outcomes per Reach Effectiveness Adoption Implementation Maintenance (RE-AIM) framework (Table 2)

Aim 3:

Secondary:

- Discussed RSV vaccination with  $\geq 1$  eligible family member or friend within 60 days of enrollment
- Implementation outcomes per Reach Effectiveness Adoption Implementation Maintenance (RE-AIM) framework (Table 2)
- Increase in RSV Vaccine confidence (BeSD indicator) by 1 point
- Increase in motivation to discuss the RSV Vaccine with eligible family members or friends(BeSD indicator) by 1 point
- Increase in confidence in the RSV Vaccine (BeSD indicator) by 1 point
- Increase in RSV vaccine knowledge by 1 point (Likert scale): Before today how much did you know about the RSV vaccine (1 = nothing, 2= a little, 3= some, 4= a lot)

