**Arm 1- Text message nudge**

**Arm 2: CHW counseling and text message nudge**

### 7.2.1.1. Procedures Aim 2

**Baseline survey:** After providing informed consent, participants will complete a 30 minute baseline survey, which will include questions on demographics, knowledge of RSV and the RSV vaccine, vaccine confidence, acculturation scale. We will use the standardized vaccine hesitancy scale and BeSD vaccine hesitancy scale.

**Intervention delivery:** The schedule of interventions is outlined in Figure 6 and outlined in the Schedule of Activities in **Section 7.3**. With texts sent 4 weeks post-enrollment in both arms and the CHW counseling within 2 weeks of enrollment.

**Endpoint survey:** Participants will receive a 60-day endpoint survey with similar questions to those asked at baseline: vaccine confidence, BeSD framework core-questions, self-reported vaccination status and location, location of vaccination, self-reported number of discussions of RSV vaccination with people  $\geq 50$  years, proportion who received text message. We will also assess implementation-specific factors: (1) Process measures (e.g. text messages received, access-related challenges in getting vaccinated, called LTF hotline), location of vaccination, access-related barriers to vaccination (i.e. challenges making an appointment) and (2) Pathways: (a) whether the interventions elicited responses along the intended pathways, e.g. did the text message positively *reinforce* or remind people to take action on intended behavior, did CHW counseling improve trust and perceptions of RSV susceptibility and (b) assess subjective rating or satisfaction of interventions by participants with Likert-style questions.

[figure not shown]
**Process Metrics/CHW log:** CHW will enter the following process measures into a log that will be entered in REDcap: fidelity to counseling script, time for each motivation session, perceived client-specific barriers and facilitators, number of calls received or made for navigation and counseling.

**Text message receipt confirmation:** Text-messages will be sent 4 weeks post-enrollment. Successful receipt will be assessed retrospectively via Twilio and self-report of reading the text will be assessed at the time of the endpoint questionnaire.

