**Ascertainment of vaccination status:** Vaccine status will be ascertained prior to text nudge and at 60 and 90 days through the medical record or California Immunization Registry (CAIR), the medical record, or proof of vaccination from a pharmacy.

**Semi-structured IDI with participants:** In accordance with principles of Grounded Theory, we will iteratively collect and rapidly analyze interview transcript data, continuing to select

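### Aim 2 mediation: trust is re-measured only at day 60 (+14), after all or most 60-day vaccinations, so an indirect effect on 60-day uptake cannot be told from vaccination raising trust

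*Protocol*

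**What the plan says.** Section 9.2 opens the Aim 2 analysis with "We will compare the primary outcome of RSV vaccine uptake within 60 days between the two study arms". Later in the same paragraph it plans formal mediation analyses of direct and indirect effects, "considering mediation by post-baseline trust and perceived benefits in the vaccine", estimated by TMLE. That sentence names neither the outcome nor the date of the mediator.

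The schedule fixes the date. Under Section 7.2.1.1, "Participants will receive a 60-day endpoint survey with similar questions to those asked at baseline: vaccine confidence, BeSD framework core-questions". Table 5 (Section 7.3) puts that questionnaire at day 60 with a window of +14 days: it may be late, not early. No vaccine-trust item is scheduled between counseling and that visit. The post-intervention rating in Section 6.2 concerns quality of delivery. The question whether counseling improved trust is part of the same late survey.

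Table 1 counts the primary outcome as 60 days from the intervention. Counseling is due within 2 weeks of enrollment, but a Table 5 footnote lets it slip to day 60.

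Section 3.2 lists two later outcomes: "RSV Vaccine uptake at 90 days per CAIR or per medical record" and "RSV Vaccine uptake at 6 months per CAIR or per medical record". Section 7.2.1.1 lists fewer checks: "Vaccine status will be ascertained prior to text nudge and at 60 and 90 days".

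Section 9.2.1 adds a nested pre/post comparison of the proportion vaccinated before the text with that 30 days after it. It does not say whether the proportions are cumulative. Participants enter unvaccinated (Table 4), and the text goes to everyone: "With texts sent 4 weeks post-enrollment in both arms".

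**The concern.** A mediator has to come before the outcome that it is said to carry. Here trust is recorded once the 60-day outcome is all or mostly settled. People who have been vaccinated may trust the vaccine more because they have had it. If counseling raises uptake by any route, for instance by easing access, the counseled arm then shows higher day-60 trust and trust goes with uptake. The analysis reads this as counseling working through trust.

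The mechanism matters to this trial. Sections 3.1 and 4.3.1 hypothesize that counseling works through trust and access, and Section 4.3.1 names community organizations and health departments as users of the result. A reversed pathway could shape what they choose to deliver.

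The pre/post-text comparison carries a smaller risk of the same kind: a rise that must happen can be taken for an effect of the text.

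**Working it through.** The plan gives no figure for this analysis, so there is none to reproduce.

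**Inputs.** From Section 9.2.1: 200 per arm, 28% uptake in the text-only arm (20% with no intervention plus 8% from the text), and a 10-point effect, hence 28% vs 38%. Assumed: the shape of the vaccination rate over time and the trust shift after vaccination. The protocol gives neither.

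**1. Share of 60-day events before the survey.**
- Clock from day 1: the earliest survey is on day 60, so the share is 100%.
- Clock from counseling on day 14 (window day 14 to 74), constant rate λ = −ln(1−p)/60, F(t) = 1−exp(−λt). With the survey on day 60 the share is F(46)/F(60): 0.2226/0.28 = 79.5% at 28% uptake and 0.3068/0.38 = 80.7% at 38%. With the survey on day 74 it is 100%.
- If vaccinations from enrollment to day 74 are counted, F(60)/F(74) gives 84% and 85%.
- If counseling slips toward day 60 the share falls further. With counseling and survey both on day 60 and events counted from enrollment, it is about 58%.

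**2. Spurious indirect effect.** Let counseling have no effect on trust, and let vaccination shift later trust M by s SD, so M ~ N(sY, 1). With p₀ = 0.28 and p₁ = 0.38, the trust density in arm a is f_a(m) = p_a φ(m−s) + (1−p_a) φ(m), and P(Y=1 | arm 2, m) = p₁ φ(m−s)/f₁(m). The apparent indirect effect is ∫ P(Y=1 | arm 2, m) [f₁(m) − f₀(m)] dm:

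| s (SD) | indirect effect | share of 0.10 |
|---|---|---|
| 0 | 0.0000 | 0% |
| 0.25 | 0.0015 | 1.5% |
| 0.5 | 0.0056 | 5.6% |
| 1 | 0.0197 | 19.7% |

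A linear product-of-coefficients simulation (n = 400, 4,000 replicates) gives 0.0, 1.5, 4.8 and 17.8%, with both paths significant in 0.2, 3.5, 6.8 and 14.2% of trials. A linear model adjusted for baseline trust gives about 3, 9 and 29% at 0.25, 0.5 and 1 SD. That model assumes baseline trust raises the log-odds of vaccination by 0.5 per SD and has a coefficient of 0.7 on later trust.

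**3. Events left after the survey.** Unvaccinated at day 60: 200×0.72 + 200×0.62 = 144 + 124 = 268, against 56 + 76 = 132 vaccinated. Expected later vaccinations (Arm 1 + Arm 2), at a constant rate or at a rate halving every 30 days and scaled to the same 60-day uptake:

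| period | constant | halving |
|---|---|---|
| day 60–90 | 21.8 + 26.4 = 48.2 | 7.7 + 9.5 = 17.2 |
| day 74–90 | 11.2 + 13.3 = 24.5 | 3.4 + 4.2 = 7.5 (rounded) |
| day 60–180 | 69.4 + 76.3 = 145.7 | 14.0 + 17.2 = 31.3 (rounded) |

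**4. Pre/post text, no text effect, 20% uptake by day 60.**
- Cumulative, day 28 to day 58: 9.9% to 19.4% at a constant rate (+9.5 points); 13.2% to 19.7% at a halving rate (+6.5 points). In Arm 1 that is 19 or 13 of 200 people.
- Equal 28-day windows, rate among the still-unvaccinated in Arm 1: 19.8 then 17.8 events, rate ratio 1.00 (constant); 26.4 then 12.4 events, rate ratio 0.52 (halving).

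**The case against.** The strongest reply is that the mediation sentence names no outcome. A separate analysis plan may choose 90-day or 6-month uptake, both already collected, and so put trust first. That stands in part: a valid version is possible, and a reader should not infer that all mediation is ruled out. But the only uptake period in that paragraph is 60 days, and no later plan can create an earlier trust measurement. For 60-day uptake the fault is fixed by the schedule.

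A reader might also infer that every 60-day vaccination precedes the survey. That holds only on the day-1 clock. Table 1 counts from the intervention, which leaves a minority after a day-60 survey, and more if counseling is late.

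The harm may be small. No document figure supports any trust shift, and at 0.5 SD or less both paths are significant in about 7% of simulated trials or fewer. This limits severity, but it does not make the estimate interpretable. The endpoint question on trust and the in-depth interviews add evidence on pathways, but neither sets the time order.

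Two stronger readings of the pre/post analyses are not supported. Section 9.2.1 neither says that its proportions are cumulative nor claims a causal effect of the text, so an automatic rise is a risk of one reading, not a stated error. For the Aim 3 pre/post analysis (Section 9.3), one might infer that discussions cannot be dated relative to the text. The full survey is not shown, so no fault is claimed there.

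**Conclusion.** The point holds for Aim 2 mediation on 60-day uptake. The mediator is recorded after all events on the day-1 clock, and after about 80 to 100% on the intervention clock with counseling by day 14 and a constant rate. Trust leading to vaccination then cannot be told from vaccination leading to trust, whatever the estimator.

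The direction of the bias rests on vaccination raising trust; its size rests on assumed shifts and on the model. It ranges from negligible to about a fifth of the effect at 1 SD, or nearly 30% in the baseline-adjusted model. A falsely significant pathway is uncommon unless the shift is large.

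These are secondary analyses and the randomized comparisons stand, so the change is one that should be made, not one on which the trial depends. The pre/post comparison in 9.2.1 is a wording point only.

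**What to change.** 1. In Section 9.2, do not report direct or indirect effects of day-60 trust on 60-day uptake. Report the relation as an association.
2. If mediation is kept, make it exploratory. Relate surveyed trust, adjusted for baseline trust, to vaccination after the actual survey date among those still unvaccinated, using the 90-day and 6-month uptake in Section 3.2. Bring the ascertainment times in Section 7.2.1.1 into line by adding the 6-month check.
3. State the price of item 2. It selects on post-randomization status, which adjustment for baseline trust only partly removes. Events are few: about 17 to 48 by day 90 if surveyed on day 60, and 7.5 to 24.5 if surveyed on day 74, against 132 within 60 days.
4. In Section 9.2.1, label the pre/post-text comparison descriptive, make no causal claim for the text, and do not use cumulative proportions, which can only rise. Equal windows remove the automatic rise but not confounding by time (rate ratio 0.52 with no text effect at the halving rate).

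The cost is wording. The survey and the registry data are already planned, and no participant contact is added.
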